### 16.3 Primary Endpoint

The primary endpoint of this trial is the response rate in terms of a clinically meaningful improvement in patient-reported fatigue at 8 weeks. A response is defined as an improvement of 2 points on the 0-10 scale of the usual fatigue on the BFI.

All patients meeting the eligibility criteria who have signed a consent form, have begun treatment, and have not had a major treatment violation within the 1st cycle of treatment will be evaluable for the primary endpoint. Patients will be analyzed according to the arm in which they were randomized.

Comparison of the primary endpoint between arms will be based on a binomial point estimate computed for each arm and a Fisher's exact test will be the inferential hypothesis test.

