### 3.0 PATIENT ELIGIBILITY

#### 3.1 Inclusion Criteria

- 3.1.1 **Age  $\geq$  18 years.**
- 3.1.2 **Diagnosed with glioblastoma, gliosarcoma, small cell or large cell glioblastoma, glioblastoma with oligo features, glioblastoma with primitive neuroectodermal tumor-like components (GBM-PNET) features, anaplastic astrocytoma, anaplastic oligodendrolioma, or anaplastic oligoastrocytoma who are clinically stable and have completed radiation therapy (excluding stereotactic radiosurgery)  $>21$  days prior to registration.** NOTE: Clinical stability will be defined as a stable or improved KPS compared to the prior month.
- 3.1.3  **$\geq 6$  score on the worst fatigue question of the BFI (Brief Fatigue Inventory, see appendix III Question 3).** It is not required for the patient to complete the entire BFI to meet this criterion.
- 3.1.4 **Undergone surgery (gross total or subtotal resection) or biopsy and will have been treated with concurrent radiation therapy and chemotherapy as standard of care for Glioblastoma, gliosarcoma, small cell or large cell glioblastoma, glioblastoma with oligo features, glioblastoma with primitive neuroectodermal tumor-like components (GBM-PNET) features, anaplastic astrocytoma, anaplastic oligodendrolioma, or anaplastic oligoastrocytoma patients.** Note: radiation must be completed per Section 3.1.2, but chemotherapy is allowed.

Patients who are currently using Optune® device will be eligible to participate in this trial.

- 3.1.5 **Negative serum pregnancy test done  $\leq 7$  days prior to registration only for women determined to be of childbearing potential by their treating physician.**
- 3.1.6 **Ability to complete questionnaire(s) by themselves or with assistance.**
- 3.1.7 **ECOG Performance Status (PS) of 0, 1, 2 or 3 (Appendix XV).**
- 3.1.8 **Provide informed written consent.**
- 3.1.9 **Willing to return to enrolling institution for follow-up (during the Active Monitoring Phase of the study).**
- 3.1.10 **Stable dose of corticosteroid  $\geq 14$  days prior to registration.**

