## 11.0 TREATMENT EVALUATION

### 11.1 Patient Self-Report Measures

The Patient self-report measures will be given three times, baseline and after weeks 4 and 8 of treatment. These items together take approximately 20 - 25 minutes to complete.

Fatigue is measured by multiple approaches in this protocol to not only provide a complete description of the type of fatigue experienced throughout treatment by the patients but also to inform future studies as to the relative merit (reliability, validity, responsiveness) the alternative methods impart in measuring fatigue.

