#### 11.1.1 Brief Fatigue Inventory (BFI)

The BFI is a 9-item instrument that allows for the rapid assessment of fatigue level in cancer patients and identifies those patients with severe fatigue. Three items ask patients to rate their fatigue for “now,” and fatigue at its “worst” and “usual” for the last 24 hours. The 11-point scales are bounded by 0 = “no fatigue” and 10 = “fatigue as bad as you can imagine.” Using the same type of scales, the remaining questions ask patients to rate how their fatigue interferes with several quality of life domains including general activity, walking, mood, work, and relations with others. These scales are bounded by 0 = “does not interfere” and 10 = “interferes completely.” The reliability and validity of the BFI were demonstrated in a study of 305 cancer patients and 290 community-dwelling adults. An internal consistency coefficient (Cronbach’s alpha) = 0.96 was demonstrated when the BFI was administered to 305 patients with cancer (80). The BFI has been demonstrated as viable primary endpoints for numerous cancer clinical trials and has been translated into 22 different languages (81).

Single-question assessment is the most commonly used and the most useful methodology. A score of 1–3 indicates the presence of mild fatigue that does not require clinical intervention, and scores of 4–6 and 7–10 indicate moderate and severe fatigue, respectively, which require further evaluation and clinical intervention (82).

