### 16.2 Sample Size

On average, we recruit six patients per month for GBM treatment trials. For symptom control studies with heterogeneous populations, such as N05C7 (Concerta), we were able to average 25 patients a month. We have found that symptom management trials targeting symptoms with a high prevalence have rapid accrual. Therefore, for this study, a reasonable conservative estimate for this more homogeneous population would be 8 patients a month. With 330 patients, accrual would be completed in 41 months.

The randomized design to be utilized is described below. Based on our previous work, we estimate that the response rate for the placebo arm will be 10%. We design the study with 100 patients per arm so that the Fisher’s exact test will have 80% power to detect a response rate of 25% with a two-tailed alternative and a 5% Type I error rate for each treatment comparison to the placebo. Again, we are not using a conservative multiple contrasts approach because we want to err on the side of accepting a modest armodafinil effect. We plan to accrue an additional 30 patients to account for patient cancellations, ineligibility, or major treatment violations. Therefore, there will be a maximum of 330 patients accrued to this study unless undue adverse events are encountered.

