## 16.5 Statistical Design

The primary endpoint for the trial is the response rate in terms of a clinically meaningful improvement in patient-reported fatigue, defined as at least a two-point improvement in fatigue as measured by the usual fatigue item from the Brief Fatigue Inventory at 8 weeks. This change

will be from baseline to 8 weeks (after randomization). The design proposed for this study will randomize a maximum of 330 evaluable patients to one of three treatment arms.

**Efficacy stopping rules:** This study will be monitored by Alliance Data and Safety Monitoring Board (DSMB) every 6 months for safety and efficacy. If at any time prior to full accrual the p-value for the Fisher's exact test that an arm is superior to the other arm given all available data falls below 0.001 then consideration will be given to stopping the trial early.

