## **16.8 Missing Data**

Routines developed by Mayo Clinic Cancer Center statisticians will be used to handle missing data in a number of ways including complete case analysis and imputation via nearest neighbor, mean value, last value, and zero value carried forward approaches. Multiple approaches are used so that the sensitivity of results to alteration in imputational assumptions may be assessed. The extent of missing data on the primary and secondary endpoints will be explored for non-random influences. Sensitivity analysis will be performed using various imputation techniques, to ensure

results are not unduly influenced by the presence of missing data. Other endpoints will be handled in a similar fashion (99).

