**Thank you for taking the time to help us.**

**APPENDIX III: BRIEF FATIGUE INVENTORY****BRIEF FATIGUE INVENTORY**

page 1 of

**Throughout our lives, most of us have times when we feel very tired or fatigued.****Have you felt unusually tired or fatigued in the last week? (check one)**

Yes \_\_\_\_\_ No \_\_\_\_\_

1. Please rate your fatigue (weariness, tiredness) by circling the one number that best describes your fatigue right NOW?

0	1	2	3	4	5	6	7	8	9	10
No fatigue										As bad as you can imagine

2. Please rate your fatigue (weariness, tiredness) by circling the one number that best describes your USUAL level of fatigue during the past 24 hours?

0	1	2	3	4	5	6	7	8	9	10
No fatigue										As bad as you can imagine

3. Please rate your fatigue (weariness, tiredness) by circling the one number that best describes your WORST level of fatigue during the past 24 hours.

0	1	2	3	4	5	6	7	8	9	10
No fatigue										As bad as you can imagine

4. Circle the one number that describes how, during the past 24 hours, fatigue has interfered with your:

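### Section 16.2 credits Fisher's exact test with 80% power at 100 evaluable patients per arm; exact calculation gives 76%, and a less conservative, baseline-stratified primary test would be a cheap improvement

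*Combined protocol and SAP*

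**What the plan says.** Response is a fall of at least 2 points on the BFI usual-fatigue item from baseline to week 8, and each armodafinil dose is compared with placebo (16.1, 16.3, 16.5). For this comparison, section 16.3 says that Fisher's "exact test will be the inferential hypothesis test".

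Section 16.2 sets 100 patients per arm and a 10% placebo response, and says that Fisher's "exact test will have 80% power to detect a response rate of 25% with a two-tailed alternative" at a 5% type I error for each comparison. It adds 30 patients for cancellations, ineligibility and major violations, which makes 330. Section 16.1 agrees: 330 accrued for 100 evaluable per arm. Section 16.5 instead describes all 330 as evaluable. Its early-stopping rule applies when the p-value of Fisher's "exact test that an arm is superior to the other arm given all available data falls below 0.001".

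Baseline usual fatigue is scheduled for every patient. The self-report measures are "given three times, baseline and after weeks 4 and 8 of treatment" (11.1), and the item asks for the number that "best describes your USUAL level of fatigue during the past 24 hours" (Appendix III). Eligibility uses a different item, at least 6 on the "score on the worst fatigue question of the BFI" (3.1.3).

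Section 5.0 commits the four stratification factors to the modelling. Section 16.4.7 permits covariates, and 16.4.8 fits a logistic model to responder status. None of these names baseline usual fatigue or alters the primary test.

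**The concern.** Fisher's test is conservative with two independent binomial samples of this size, so a round 80% at a round 100 per arm suggests that the sample size came from a normal approximation. If so, the chance of missing the design effect is larger than the plan states. That also sits badly with the sponsor's reason for not adjusting for multiplicity, which is a wish to lean towards accepting a modest effect.

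The endpoint is also defined relative to baseline usual fatigue, so that score is linked to response by construction. A patient who starts at 0 or 1 cannot respond at all. The score is collected anyway, and the primary test makes no use of it beyond the change itself.

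**Working it through.** **Inputs.** From 16.2: n = 100 evaluable per arm, p0 = 0.10, p1 = 0.25, two-sided α = 0.05. From 16.3 and 16.5: response is a fall of 2 points or more on usual fatigue.

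**1. Where the 80% comes from.** Pooled-z formula without continuity correction, with mean rate 0.175:

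n = [1.960·√(2·0.175·0.825) + 0.842·√(0.10·0.90 + 0.25·0.75)]² / 0.15² = [1.053 + 0.443]² / 0.0225 ≈ 99.5, so 100 per arm.

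Power at n = 100: Φ[(0.15·√100 − 1.053)/0.527] = Φ(0.848) = 80.2%.

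The plan's figure is reproduced, but for a test that it does not name. With continuity correction the same formula asks for 113 per arm.

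**2. Power of the named test.** Sum the product of the two binomial probabilities over every table (x0, x1) with two-sided Fisher p ≤ 0.05:

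| Test, 10% vs 25% | n per arm | Power | Size |
|---|---|---|---|
| Fisher | 100 | 76.2% | 2.9% (at 10%) |
| Fisher | 109 | 79.9% | |
| Fisher | 110 | 80.4% | |
| Boschloo, unstratified | 100 | 79.2% | 4.96% (maximum) |
| Pearson chi-square | 100 | 81.6% | 5.2% (at 10%) |

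Doubling the one-sided Fisher p-value also gives 76.2%. The shortfall is 80 − 76.2 = 3.8 points. Replacing Fisher by plain chi-square adds 81.6 − 76.2 = 5.4 points.

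**3. What baseline adds.** The documents give no mean, SD or baseline/week-8 correlation for usual fatigue, so these are assumed. Scores are rounded to 0-10, and the week-8 mean is shifted so that the response rates are 10% and 25%. There are 100 patients per arm, bands 0-3/4-6/7-10 and 20,000 simulated trials per setting. Entries are power of uncorrected CMH / unstratified chi-square, in %:

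| Correlation | Mean 5, SD 2 | Mean 6, SD 2 | Mean 6, SD 1.5 |
|---|---|---|---|
| 0.3 | 86.1 / 81.1 | 85.0 / 80.9 | 85.3 / 81.0 |
| 0.5 | 84.3 / 81.4 | 84.0 / 81.5 | 84.1 / 81.4 |
| 0.7 | 83.0 / 81.5 | 82.9 / 81.5 | 83.0 / 81.6 |
| 0.85 | 82.1 / 81.5 | 81.8 / 81.5 | 82.1 / 81.4 |

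Baseline adds 0.3 to 5.0 points over chi-square. CMH size was 4.7-5.0%. A repeat of the simulation reached 86.8%, so 82-87% is a fair range.

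**4. Variants that do less well.**
- CMH with continuity correction: about 76-82%.
- Exact stratified test, probability-ordered p-value: 79.2-83.4% (size 3.6-3.9%).
- Exact stratified test, tail-doubled p-value: 76.6-81.1%.
- Baseline not prognostic: uncorrected CMH 80.6-80.8% against 81.4% for chi-square in the same runs; exact versions 77.8-78.0% and 75.4%.

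**5. Plausibility of the larger gains.** At correlation 0.3, a 10% placebo response requires mean placebo fatigue to worsen by about 0.8 (SD 1.5) to 1.5 points (SD 2). A placebo-controlled methylphenidate trial described in 1.2.1 saw improvement in both groups. In the settings where the placebo mean is roughly unchanged, baseline adds only 0.3-1.4 points.

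**6. Stopping rule.** At 50 per arm and 10% versus 25%, p < 0.001 occurs in 5.9-6.0% of trials with Fisher and 8.1-8.5% with CMH. The two disagree in 3.4-4.3% of trials. Under the null, at 30-100 per arm, both stay below 0.08%.

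**The case against.** The strongest reply is that an unadjusted Fisher test on a binary endpoint is valid, that the trial seeks only preliminary efficacy (2.1), and that the endpoint is already a change from baseline. All of this stands. What follows is a loss of efficiency; nothing here makes the test improper.

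A second reply is that 330 evaluable patients (16.5) means 110 per arm, where Fisher does have 80.4%. The arithmetic is right, but 16.1 and 16.2 both make 330 the total accrual for 100 evaluable per arm, and 16.2 attaches its power claim to 100. The sections need reconciling; the sentence in 16.5 does not rescue the one in 16.2.

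A third is that most of the gain needs no baseline at all. This also stands: chi-square alone gives 81.6%, with no bands and no assumed correlation.

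Two stronger readings are tempting. A reader might infer that stratifying on baseline always restores 80%. It does so for the uncorrected asymptotic CMH in every setting examined, but not for the continuity-corrected or exact versions. A reader might also infer that the eligibility score pins down baseline usual fatigue because both items recall 24 hours. The documents do not support that. Eligibility is scored before registration, while the baseline booklet may be completed up to 14 days after it (4.0, note 6), so the two windows need not coincide.

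**Conclusion.** The power statement in 16.2 is wrong as written: for the named test, at the stated inputs, it is 76.2%. The risk of missing a 25% response is therefore about 24% per comparison instead of 20%. This part uses only the plan's own numbers.

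The change of primary test is worth considering and is not required. Leaving Fisher is worth about 5 points. Baseline is worth about 0-5 more, and that part depends on the assumed mean (5-6), SD (1.5-2) and correlation (0.3-0.85). If baseline proves non-prognostic, stratifying costs about 1 point against chi-square. The documents do not support saying that the primary analysis is invalid, or that omitting baseline is the main cause of the lost power; Fisher's conservatism alone accounts for the gap from 80%.

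**What to change.** 1. **16.2:** restate Fisher's power at 100 per arm as about 76%. If Fisher stays primary and 80% is wanted, it needs 110 evaluable per arm.
2. **16.5 against 16.1 and 16.2:** reconcile whether 330 is total accrual or the evaluable number.
3. **16.3 (optional):** make the primary test for each dose versus placebo a CMH test, stated to be without continuity correction. Stratify by pre-specified baseline usual-fatigue bands, for example 0-3/4-6/7-10, following 11.1.1, where 4-6 and 7-10 "indicate moderate and severe fatigue, respectively". Report the Mantel-Haenszel risk difference with 95% CI, and keep Fisher as a sensitivity analysis. The simpler alternative is an unstratified chi-square, or Boschloo's test if exact size control is wanted.
4. **16.5:** state which p-value the 0.001 rule uses. Leaving it on Fisher is acceptable if said.
5. **16.8:** if bands are used, say how a patient with a missing baseline score is banded. The section lists "imputation via nearest neighbor, mean value, last value, and zero value carried forward approaches" and gives no such rule.

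The cost is a few sentences and analysis code, with no new patients or data unless item 1 is met by enlarging the arms. The price of item 3 is loss of exact size control (simulated size about 5%). The exact stratified version keeps that control but does not always reach 80%.

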## 16.4 Secondary Endpoints

**16.4.1 Other time points:** The same analyses carried out using the 8 week assessment data will be used for analysis of data from the other time point assessments.

**16.4.2 Other fatigue measures:** The other fatigue items ("usual", "usual" and "now") as well as the impact of fatigue items from the BFI, the PRO-CTCAE, and the summated score from the PROMIS fatigue measure will be analyzed separately in turn comparing the average of these variables for each treatment using Kruskal-Wallis testing for change from baseline to four weeks, AUC over the entire treatment period, and repeated measures ANOVA using all treatments and all time points.

**16.4.3 Cognitive function:** The same analyses outlined for the other fatigue measures will be carried out for each of the cognitive function tests.

**16.4.4 Quality of life:** The same analytical approaches will be used to compare the three treatments in terms of QOL as was outlined for the other fatigue measures.

**16.4.5 Safety and tolerability of armodafinil:** Comparison of the proportion of patients reporting adverse events via the CTCAE items will be compared across treatment arms using a Fisher's exact test.

**16.4.6 Area under the curve (AUC) and summary statistics:** For the continuous measures mentioned above, AUC summary statistics will be generated for each patient to represent the overall experience reported by patients for each endpoint (e.g. fatigue) by combining the data from baseline, weeks 4, and 8 assessment points. The average of these AUC variables will be compared between the two treatment arms using two-sample t-tests. Further summary statistics will be constructed for the categorical variables to indicate whether the patient ever responded over the entire treatment period. These categorical variables will be compared between treatment groups via Fisher's exact tests.

**16.4.7 Repeated measures analysis:** The overall experimental layout will be examined via the construction of a repeated measures model using data from all assessment time points involving the continuous variables described above. Tests for time by treatment interaction will be carried out by the profile analysis methods of Srivastava. Covariates such as age, gender and other clinical variables may be included to test their impact on the initial efficacy tests of the primary and secondary analyses described above. Use of the Optune® device will also be included as a descriptive factor.

**16.4.8 Logistic regression analysis:** The overall experimental layout will be examined via the construction of a logistic regression model using the categorical response variables described above. This will allow for the characterization of the demographic and clinical variables' impact on the identification of a patient as a responder per the above definition.

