#### 2.2 Secondary

- 2.2.1 To evaluate the tolerability at 8 weeks of 150mg and 250mg armodafinil in this patient population**
- 2.2.2 To assess the effect of armodafinil at 8 weeks on cognitive function in patients with high grade glioma.**
- 2.2.3 To assess the impact of armodafinil on global quality of life and other fatigue endpoints in this patient population with high grade glioma.**
- 2.2.4 Explore the correlation between the BFI, PROMIS, and PRO-CTCAE measures, as well as, the relationship of fatigue and cognitive difficulties.**

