#### 4.0 TEST SCHEDULE

Test Schedule Table

	Active-Monitoring Phase			
	≤28 days prior to registration	Baseline	End of Week 4 (Cycle 1)	End of Week 8 (Cycle 2)
General neurological exam, weight, performance status	X			
Pregnancy test	X 			
Performance status			X 	X 
Neurocognitive testing (Appendix VII)		X 	X 	X 
Adverse event assessment		X	X	X
Patient Questionnaire Booklet 
 
• Brief Fatigue Inventory (BFI)
 
• PROMIS
 
• PRO-CTCAE (for fatigue and cognition items)
 
• Linear Analogue Self-Assessment (LASA)
 
• FACT-Cog
 
• Godin Leisure Time Exercise Questionnaire (GLTEQ)
 
 (Appendices III-VI, XIII, XIV)		X 	X 	X 
Nurse/CRA Phone Contact (Appendix XII)			X	X

1. If the treating physician determines that the woman is of childbearing potential, then a pregnancy test must be done  $\leq$  7 days prior to registration.
2. Patient questionnaire booklets **must** be used; copies are not acceptable for this submission.
3. Must be administered by credentialed personnel. See section 4.1 and appendices VIII and IX.
4. PS will be collected via the Nurse/CRA Phone Contact.
5. Administered at the end of weeks 4 and 8.
6. Baseline assessment must be done  $\leq$  14 days after registration and no more than 7 days prior to 1st day of study drug.
7. +/- 3 days, timing for week 4 and 8 assessments should be measured from time of study drug administration – not baseline.

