## **11.2 Objective Cognitive Measures (Primary Cognitive Endpoint)**

The neuropsychological battery proposed for this study overlaps with batteries used in numerous North Central Cancer Treatment Group (NCCTG) multi-center trials for studies in patients with CNS tumors without any problems or complications.

Clinicians and researchers must balance the often conflicting goals of obtaining valid PRO data while not burdening patients or interfering with the provision of care in a busy clinical setting. When surveyed about the preferred properties for an assessment battery for neurological and behavioral function, 191 experts in clinical and epidemiologic research reported it should be brief, precise, and easy to administer, score, and interpret (93).

The Symbol Digit Modalities Test (SDMT; Smith, 1982) is a measure of attention, visual tracking, and psychomotor speed. The task consists of a brief practice, followed by a 90-second test trial. Subjects are given a key in which 9 symbols are paired with each of the digits 1 through 9. Below the key is a grid in which a random series of the symbols appear above empty boxes. The task is to fill in the correct digit under each symbol, without skipping boxes, as quickly as possible for 90 seconds. This task has been found to be a particularly sensitive indicator of brain dysfunction (95).

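### Goal 2.2.2 asks about cognition at 8 weeks, but the only single-visit comparison of arms specified for the cognitive tests is at 4 weeks

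*Combined protocol and SAP*

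**What the plan says.** Goal 2.2.2 (section 2.2) reads: "To assess the effect of armodafinil at 8 weeks on cognitive function in patients with high grade glioma". Section 11.2 gives the objective tests a leading role in its title: "Objective Cognitive Measures (Primary Cognitive Endpoint". The test schedule (section 4.0) marks them for baseline and for both later visits, with the footnote "Administered at the end of weeks 4 and 8".

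The analysis is set by reference. Section 16.4.3 says: "The same analyses outlined for the other fatigue measures will be carried out for each of the cognitive function tests". In 16.4.2 those analyses are a rank test, "comparing the average of these variables for each treatment using Kruskal-Wallis testing for change from baseline to four weeks", then AUC over the treatment period, then repeated measures ANOVA on all visits. For the repeated measures model, 16.4.7 names one test: "Tests for time by treatment interaction will be carried out by the profile analysis methods". Section 16.4.1 adds: "The same analyses carried out using the 8 week assessment data will be used for analysis of data from the other time point assessments".

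Two wording problems lie in the same section. The item list in 16.4.2 begins "The other fatigue items ('usual', 'usual' and 'now", so one item appears twice and *worst* is absent. Section 16.4.6 compares AUCs by two-sample t-test between two treatment arms, in a trial with three.

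**The concern.** Followed literally, the plan answers a 4-week question with the only single-visit test that the cognitive measures receive. That test can miss an effect that is still building, or report one that has gone by the visit named in the goal. Without a prespecified week-8 comparison, the choice of which visit and which contrast to report for cognition is left until the data are in hand.

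The list in 16.4.2 repeats *usual*, which is already the primary item (16.3), and so leaves *worst*, the entry item (3.1.3), out of the section 16.4 analyses.

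**Working it through.** **Step 1. Is a week-8 comparison of arms specified for cognition?** Each candidate in turn:

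- *Kruskal-Wallis test (16.4.2)*: change to week 4 only.
- *AUC (16.4.2, 16.4.6)*: uses week 8, but pooled with the other visits. No formula is given. If it is a trapezoid over weeks 0, 4 and 8, the weights are 2, 4 and 2, so week 8 carries 2/8 = 25%, the same as baseline.
- *Repeated measures ANOVA and profile test (16.4.2, 16.4.7)*: use week 8. The named test asks whether the profiles differ in shape. A week-8 contrast could be taken from the model, but none is named.
- *Section 16.4.1*: carries analyses of week-8 data to other visits. For cognition no week-8 analysis is written for it to carry, and 16.4.2 says four weeks explicitly.

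So week-8 data are used, but no week-8 comparison is prespecified. The conflict with a stated goal is confined to cognition, because goal 2.2.3 (quality of life and other fatigue endpoints) names no visit.

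**Step 2. What could this cost?** The plan gives no power figure for cognition, so there is none to reproduce. The only input from the documents is 100 evaluable patients per arm (16.2). Assumed: SD 1 at every visit, equal correlation r = 0.3/0.5/0.7 between visits, the same effect in both armodafinil arms, normal scores, two-sided 5%.

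The variance of a change score is 1 + 1 − 2r = 2(1 − r) = 1.4/1.0/0.6. With arm effects 0, δ, δ the squared deviations from their mean 2δ/3 sum to (4/9 + 1/9 + 1/9)δ² = (2/3)δ². For the three-arm Kruskal-Wallis test (2 df, critical value 5.99) the approximate noncentrality is

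λ = (3/π) × 100 × (2/3)δ² / [2(1 − r)].

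- δ = 0.2: λ = 1.82/2.55/4.24, power about 21/28/44%.
- δ = 0.4: λ = 7.28/10.19/16.98, power about 67/82/97%.

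For the profile test (4 df), with effects d4 and d8 at the two visits,

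λ = 100 × (2/3) × 2(d4² − d4·d8 + d8²) / [3(1 − r)].

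With d4 = 0.2 and d8 = 0.4, λ = 7.62/10.67/17.78 and power is about 58/75/94%.

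Simulation (20,000 trials per setting) agrees:

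| Effect in SD (week 4, week 8) | Week-4 test | Week-8 test |
|---|---|---|
| Building (0.2, 0.4) | 21/27/43% | 67/82/96% |
| Complete by week 4 (0.4, 0.4) | 67/81/97% | 67/82/96% |
| Fading (0.4, 0.2) | 66/82/96% | 20/27/43% |

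The simulated profile test has 58/74/94% in the building case. Its formula is symmetric in d4 and d8, so building and fading effects give the same λ. A positive result cannot tell them apart, which is why it does not replace a week-8 estimate.

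**Step 3. Fewer patients at week 8.** Patients who stop the agent before 8 weeks go off study (13.0). For a 0.4 SD week-8 effect, simulation (10,000 trials) gives the week-8 test 59/74/93% with 85 per arm and 50/67/87% with 70.

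**The case against.** The strongest reply is that the plan does not neglect week 8. The data enter three planned analyses. In the building case the profile test is only 9/8/2 points below a week-8 rank test (67 − 58, 82 − 74, 96 − 94). Section 16.4.1 can also be read as treating week 8 as the default visit throughout. Most of this stands. A reader might infer that week-8 cognitive data go unanalysed, or that a large loss of power has been shown; the documents support neither. What remains is that the effect named in the goal has no prespecified comparison, and the generous reading of 16.4.1 still collides with the explicit four weeks in 16.4.2.

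A reader might also infer that 16.4.6 leaves the compared arms open. Section 16.1 largely settles this: endpoints are compared for each armodafinil arm against placebo in turn. Only the wording needs aligning.

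Nor is the *worst* item unused everywhere: Appendix X defines response for the shadow design on it. It is missing from 16.4.

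Finally, the unadjusted AUC comparison might look biased. Under randomisation it is valid, and adjusting for baseline would only add precision.

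**Conclusion.** The point holds as a mismatch between a stated goal and the analysis assigned to it. It should be corrected, but it concerns secondary analyses and leaves the primary endpoint untouched. The mismatch rests on the text alone. Its size rests on the effect sizes, correlations and time courses assumed above: from no loss of power, if the effect is complete by week 4, to a fall from 67/82/96% to 21/27/43% for the change-score test, if the effect builds linearly.

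The documents do not favour one course. Section 15.1.5 puts drug steady state at about 7 days, which says nothing direct about cognition. With attrition and an early effect, week 8 would be the weaker visit. The reason to name it is that the goal asks about it, not that it always has more power. The item list and the AUC wording are plain text corrections.

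**What to change.** - **16.4.3**: name change from baseline to week 8 as the lead comparison for each cognitive test. Keep the planned three-arm Kruskal-Wallis test, follow it with each armodafinil arm versus placebo as in 16.1, and make week 4 supportive. The rank test suits Trail Making: runs stopped at the 3- or 5-minute limit (Appendix VIII) have no completion time but can be ranked last. The text should state that rule, including for runs stopped at baseline. A baseline-adjusted estimate may be added as support for tests without a time cap.
- **16.4.2**: change the item list to *worst* and *now*.
- **16.4.6**: replace the reference to two treatment arms with each armodafinil arm versus placebo. Baseline adjustment of the AUC is optional; if adopted, it applies to every AUC that 16.4.6 covers, including fatigue and quality of life.

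The cost is text in section 16. The tests are already given at baseline, week 4 and week 8, so no new data or patients are needed. There are two downsides. Each cognitive test gains two pairwise contrasts. Week 8 may also have fewer data than week 4, so the missing-data sensitivity analyses in 16.8 should explicitly cover this comparison. The repeated measures and profile analyses stay as planned.
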